Advances in AI-enabled deep learning for CT image analysis allow automated identification of parenchymal lung changes, quantitative segmentation of hypo-ventilated or high-density regions, and integration with clinical data to build predictive models. Incorporating multicentre data can improve model generalizability and address the performance decline often observed in external validation of single-centre studies, thereby supporting the development of robust and reliable intelligent auxiliary strategies for ARDS diagnosis and management. Indeed, the high mortality associated with ARDS stems not only from inadequate management strategies but also from challenges in early detection, risk stratification, and severity prediction. Consequently, developing AI-assisted diagnostic and management tools represents a pressing need, particularly for critical conditions such as ARDS [29–31].

Therefore, this study proposes a multicentre retrospective investigation integrating data from 400 ARDS cases across three tertiary comprehensive hospitals. Through standardized image preprocessing and rigorous modeling approaches, we aim to develop and validate a CT-imaging-driven model for ARDS grading and clinical decision support, assess its cross-centre stability, and ultimately provide a generalizable intelligent tool for clinical practice.

Primary Objective

To develop an intelligent assessment model for ARDS severity using multicentre chest CT data. By integrating quantitative CT features with clinical characteristics, the

model aims to predict short-term major clinical events (such as decisions regarding mechanical ventilation, prone positioning strategy, mortality, and ECMO use), stage and quantify the disease, and establish a diagnostic and risk-stratification model for ARDS to assist in guiding therapeutic strategies.

Secondary Objective

To validate the generalizability of the model across external centres and evaluate its applicability in multicentre real-world settings; and to analyze the influence of different centres and CT scanner models on imaging features and model performance.

The overall research design and plan

This was a retrospective, multicenter, observational cohort study.

Study population

This study planned to enroll a total of 400 ARDS patients admitted to the intensive care units of three comprehensive tertiary hospitals.

Inclusion Criteria

1. Patients meeting the **2023 global updated definition of ARDS**.

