The proposed lung-segmentation DL model will accept lung-masked CT images as input (images cropped, masked, and rescaled to include the whole lung and lesions). The model outputs segmentation masks for left and right lungs, lobes, bronchopulmonary segments, and lesion types including ground-glass opacities (GGO), consolidation, and atelectasis. Anatomically, there are typically 18–20 bronchopulmonary segments; because segment-level granularity can complicate

downstream analysis, we will simplify segmental mapping into four bilateral segments and define 11 lung regions for analysis: right upper, right upper-middle, right lower-middle, right lower, whole right, left upper-middle, left lower-middle, left lower, whole left, and whole lung. By computing the proportion of lesion volume in each lung region, we will derive a structured set of imaging features reflecting regional lung involvement.

Interpretable Severity Assessment

Because segmentation results provide the primary evidence for severity assessment, we propose a multi-task architecture with separate task heads for segmentation and for lesion-severity evaluation. In this way, the segmentation DL model becomes a multi-task model capable of both precise lung/lesion segmentation and quantitative severity scoring; moreover, the segmentation outputs improve model interpretability for clinicians.

Using the above lung-segmentation model, we will compute the following quantitative metrics to characterize CT-detected disease burden:

- ① Absolute lesion volumes for the whole lung, each lobe, and each defined bronchopulmonary region.
- ② Percent lesion volumes for the whole lung, each lobe, and each bronchopulmonary region (i.e., lesion volume divided by region volume), used to quantify ARDS severity and lesion distribution.
- ③ Histograms of CT attenuation values (in Hounsfield units, HU) for different lesion regions.

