The inference pipeline of the multi-task model is as follows: chest CT scans are input to the DL segmentation system, whose segmentation head(s) generate masks for lesion regions, whole lung, lobes, and bronchopulmonary regions. Quantitative metrics are then calculated from the segmentation masks to quantify each patient's lesion burden and to form a feature vector of regional involvement. These imaging features are projected into the DL model's latent feature space and used by the severity-assessment head to predict disease severity. This design enables end-to-end prediction while preserving explainability through explicit regional segmentation outputs.

4. Etiological and Respiratory Mechanics Classification

[figure not shown]
As noted above, existing approaches are limited in their ability to process multimodal data simultaneously, which restricts the model's capacity to integrate all

patient-level features. The Transformer architecture employed in this study is inherently well suited for multimodal learning and has been widely applied across natural language processing, computer vision, and cross-modal tasks. Representative examples such as GPT-4, CLIP, and BLIP demonstrate the capability of Transformer-based models to learn a unified feature space for both text and images, enabling joint understanding of heterogeneous inputs.

Building upon the ARDS severity-assessment DL model described earlier, we further extend the framework to incorporate patient etiology and respiratory mechanics parameters to enable a more comprehensive and accurate prediction. Specifically, the encoder of the DL model is used to extract high-level features from CT scans, while a tokenizer is applied to encode structured clinical variables. The tokenizer may be initialized using models trained on large text corpora, such as a BERT tokenizer or a CLIP tokenizer.

Because imaging and clinical variables naturally reside in different feature spaces, the model cannot directly process them in their raw form. To address this, we introduce learnable linear projection layers for each feature type, mapping all inputs into a unified latent space. The multimodal features are then concatenated and fed into the prediction head to estimate ARDS severity and classify physiologic or etiologic subtypes based on the full spectrum of patient characteristics.

5. The overall process of the U-Net model

Sample size estimation

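### Read literally, the plan lets the model take as inputs variables that define the severity grade or reveal the treatments scored in primary outcomes 1 and 2

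*Combined protocol and SAP*

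**What the plan says.** The plan describes two routes to a severity output.

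- **CT route.** Under Construction of a Deep-Learning Lung Segmentation Model, the input is images: "The proposed lung-segmentation DL model will accept lung-masked CT images as input". Interpretable Severity Assessment gives the reason, that "segmentation results provide the primary evidence for severity assessment". The regional imaging features are then "used by the severity-assessment head to predict disease severity".
- **Multimodal route.** Section 4 builds on that model: "we further extend the framework to incorporate patient etiology and respiratory mechanics parameters". CT features come from the encoder, while "a tokenizer is applied to encode structured clinical variables". The combined features are "fed into the prediction head to estimate ARDS severity and classify physiologic or etiologic subtypes based on the full spectrum of patient characteristics".

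The aims point both ways. The Introduction sets out to develop and "validate a CT-imaging-driven model for ARDS grading and clinical decision support". The Primary Objective begins "By integrating quantitative CT features with clinical characteristics" and goes on to staging the disease and predicting events that include ventilation and prone-positioning decisions.

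Primary outcome 1 compares predicted severity with the clinical grade under the 2023 global criteria, using CT from the first 24 hours in the ICU. Primary outcome 2 compares recommended with actual management at the index CT over five modalities: mechanical ventilation, high-flow oxygen, non-invasive ventilation, prone positioning and neuromuscular blockade.

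The Data collection list has receipt of mechanical ventilation, high-flow oxygen and ECMO under baseline clinical data, SpO2 under physiologic parameters, PaO2 and FiO2 under laboratory parameters, and PEEP, tidal volume, plateau pressure and flow under ventilator or high-flow parameters.

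**The concern.** A prediction result is informative only if the inputs do not already contain the answer. If the head scored for primary outcome 1 is given the variables from which the reference grade was assigned, its accuracy partly measures how well it reconstructs the clinical rule and not what CT contributes. If the treatment model is given a field saying that the patient was ventilated, or a set of ventilator settings, agreement on that modality can be read from the input row.

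The external test set would not expose this if its cases carry the same variables, because the shortcut works equally well there. The effect could also spread. The Statistical Analysis Plan puts agreement between recommended and actual treatment into multivariable logistic models, and the secondary outcomes relate that agreement to 28-day in-hospital mortality. Agreement that comes from reading the label would change the meaning of those odds ratios.

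**Working it through.** The plan gives no figure on this point, so the check sets its statements side by side.

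**1. Severity (primary outcome 1).**
- Which head is scored? The outcome definition refers to severity predicted by the model from CT. Both heads take CT, so this leans towards the CT route without settling it. The Statistical Analysis Plan names the severity task but not its inputs.
- Could PaO2, FiO2 and SpO2 enter the multimodal head? The additions named in section 4 are etiology and respiratory mechanics, which do not plainly cover oxygenation. Three broader statements do: the reference to all patient characteristics, the encoding of structured clinical variables, and the Primary Objective's use of clinical characteristics to stage disease.
- Would they disclose the label? Only if the reference grade depends on oxygenation. The protocol prints no cut-offs, so this is an assumption.

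**2. Treatment matching (primary outcome 2).**
- Receipt of two of the five scored modalities, mechanical ventilation and high-flow oxygen, is filed as baseline data. Receipt must be collected in any case to form the label, so collecting it is not the fault.
- PEEP, tidal volume, plateau pressure and flow can reveal which device was in use, by their values or by being blank. They are also the listed variables closest to the respiratory mechanics that section 4 adds.
- The multimodal head in section 4 outputs severity and subtypes, not treatment. The link to the treatment model therefore comes from the Primary Objective, which predicts ventilation decisions using clinical data, and is an inference.

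**3. Timing.** The treatment label is fixed at the index CT. Receipt carries the word baseline, which indicates a time but is not defined. The device settings carry no time. No visible text requires predictor values to be dated at or before the index CT.

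**4. Other input statements.** The only stepwise description of inputs in the Statistical Analysis Plan, adding severity and then treatment information, concerns mortality. It does not govern the severity or treatment tasks.

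**5. Illustration only.** The documents give neither a match rate nor a scoring rule. Suppose matching is averaged over five modalities, q is the match probability without leakage, and k labels are recovered from the inputs with probability r. The gain is [k·r + (5 − k)·q]/5 − q = k(r − q)/5.

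| Assumed case | q = 0.5 | q = 0.7 | q = 0.9 |
|---|---|---|---|
| k = 2, r = 1 | 0.4 × 0.5 = 0.20 | 0.4 × 0.3 = 0.12 | 0.4 × 0.1 = 0.04 |
| k = 1, r = 1 | 0.2 × 0.5 = 0.10 | 0.2 × 0.3 = 0.06 | 0.2 × 0.1 = 0.02 |
| k = 2, r = 0.9 | 0.4 × 0.4 = 0.16 | 0.4 × 0.2 = 0.08 | 0.4 × 0 = 0.00 |

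The range, 0 to 20 percentage points, follows from the assumed values and estimates nothing about this study. No comparable illustration is possible for severity without the grading rule.

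**The case against.** The strongest reply is that the relevant content may simply be out of sight. The figure in section 4 is not shown and section 5 on the overall U-Net process has no visible text. Those are natural places for a diagram of inputs and heads, and absence alone cannot carry the point. This stands. What remains is the positive wording: a severity estimate from all patient characteristics, and clinical data used to stage disease and predict ventilation decisions, set beside a collection list that contains the revealing variables.

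Second, treatment data have other stated uses: as outcome labels, as a later addition to the mortality model, and in the LASSO analysis of intervention-related variables. This also stands. A reader might infer that receipt is fed to the treatment model, but no visible text says so.

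Third, the plan leans towards CT for severity. That is right, and if the CT-only head is the one scored, the severity half falls away. The multimodal objective keeps the other reading open.

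Fourth, the planned interpretability analyses could show reliance on such variables, and the validation set would allow this to be checked during development. That is possible, since the plan does not say when they are run. It also does not say that the model would then be changed.

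Fifth, respiratory mechanics were added on purpose, so removing every setting from every task would go further than the problem requires. This is accepted and limits the fix.

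**Conclusion.** The concern holds as a risk created by the visible wording. Followed literally, the text allows both primary outcomes to be read in part from the model's own inputs, and no visible statement prevents it. The severity half rests on two conditions: that the multimodal head is the one scored, and that the reference grade depends on oxygenation. The treatment half rests on reading the Primary Objective's clinical characteristics to include receipt or device settings.

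Two stronger readings are tempting and not supported. One is that leakage has been shown or that the primary results will be invalid; the documents do not show which variables enter which head. The other is that the multimodal severity model should give way to the CT model. Integrating CT with clinical data is the stated objective, and the difficulty is confined to variables that define or reveal the label being scored.

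The size of any inflation cannot be computed from the documents. Confidence is medium because of the content that cannot be seen.

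**What to change.** In the modelling section and the Statistical Analysis Plan:

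1. For any severity result scored against the reference grade as primary outcome 1, list the variables that define that grade and exclude them from the inputs. The CT-only head already meets this. Report the full-input multimodal result alongside it.
2. For treatment matching, exclude receipt of the scored modalities. Exclude PEEP, tidal volume, plateau pressure and flow, with their missingness indicators, at least when scoring the modalities they reveal: mechanical ventilation, high-flow oxygen and non-invasive ventilation. For prone positioning and neuromuscular blockade, report results with and without the settings.
3. Use only predictor values timed at or before the index CT, and define baseline accordingly.

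If the unseen figure or section 5 already imposes these limits, a sentence in the text saying so is enough. Otherwise the cost is the wording, one retraining with masked inputs, and possibly less favourable accuracy and matching rates.

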2. Admission to the **Intensive Care Unit (ICU) for more than 48 hours**.
3. Availability of **chest CT imaging data**.

Exclusion Criteria

1. Patients aged <18 years.
2. Patients with incomplete medical records.
3. Absence of chest CT imaging or presence of technically inadequate/uninterpretable chest CT images.

Sample Size and Data Partitioning

This study is designed as a multicenter, large-sample, retrospective observational study and plans to include a total of 400 patients with ARDS who meet the eligibility criteria. Of these, 300 cases will be contributed by the primary institution and Sub-center 1, and 100 cases by Sub-center 2.

The study does not involve conventional experimental or control groups. Instead, cases will be partitioned into three datasets according to the model development workflow:

Training set: 276 cases (approximately 80% of the combined cases from the primary institution and Sub-center 2), obtained through stratified random sampling to preserve the distribution of mild, moderate, and severe ARDS;

Internal validation set: 69 cases (approximately 20% of cases from the same two centers), used to monitor overfitting and optimize model hyperparameters;

External test set: 55 cases, all derived from Sub-center 1 and entirely independent of the model development process, used to evaluate model generalizability.

Primary Outcome Measures

The primary outcomes of this study focus on the overall effectiveness of the proposed AI-based framework across three key clinical tasks:

(1) Accuracy of ARDS severity classification, defined as the agreement between model-predicted ARDS severity (mild, moderate, or severe) and the reference clinical classification based on the 2023 global ARDS criteria, assessed using chest CT images obtained within 24 hours of ICU admission;

(2) Treatment plan matching rate, defined as concordance between model-recommended and actual clinical management across five intervention modalities (mechanical ventilation, high-flow oxygen therapy, non-invasive ventilation, prone positioning, and neuromuscular blockade), evaluated at the time of index chest CT acquisition;

(3) Accuracy of 28-day in-hospital mortality prediction, defined as the ability of the model to predict all-cause in-hospital mortality within 28 days of ICU admission.

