The sample size was preliminarily estimated using the event-per-variable principle. The mortality prediction component is designed to include no more than 15 candidate predictors in the final multivariable logistic regression model. Following the commonly accepted criterion of at least 10 outcome events per predictor, a minimum of 150 death

events is required to ensure model stability and interpretability. Based on historical data from the participating centers, the in-ICU mortality rate among patients with ARDS is approximately 37.5%. Accordingly, the total target sample size for this study is estimated to be approximately 400 patients.

Statistical Analysis Plan

All eligible cases will be stratified and randomly sampled at an 8:2 ratio within Shanghai General Hospital and its affiliated centers to form the model training set and internal validation set. Cases from an additional participating center will be reserved as an independent external test cohort.

Model performance will be evaluated for three predefined tasks: ARDS severity classification, treatment strategy prediction, and mortality risk prediction. Performance metrics will include accuracy, balanced accuracy, area under the receiver operating characteristic curve (AUC), precision–recall curve analysis, and the Brier score. During model development, five independent repeated experiments will be conducted, and performance will be reported as mean values with standard deviations.

For comparative performance assessment, results from the five independent experiments will be compared using two-sided Wilcoxon rank-sum tests, with a significance threshold of 0.05. Different levels of statistical significance will be denoted using conventional symbols (e.g., “*”, “**”) corresponding to predefined P-value ranges.

To assess the association between model outputs and clinical outcomes, model-recommended intervention sets will first be encoded for agreement with actual clinical management. These agreement variables will then be incorporated into multivariable logistic regression models together with six imaging-derived anatomical features (e.g., diaphragmatic height, lung volume). Adjusted odds ratios with 95% confidence intervals will be reported, and a two-sided P value <0.05 will be considered statistically significant.

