For mortality risk prediction, ARDS severity classification and treatment strategy information will be sequentially added to the input features to evaluate their incremental impact on balanced accuracy and Brier score. Model calibration and discrimination will be assessed using calibration curves and precision–recall curves. In addition, least absolute shrinkage and selection operator (LASSO) regression will be applied to all structural, pathological, and intervention-related variables, and standardized coefficients will be extracted to facilitate interpretation of key risk-driving factors across different ARDS severity strata.

Ethics and Informed Consent

This study is a multicenter, retrospective, observational study involving the secondary use of previously collected clinical and imaging data. The study protocol, informed consent materials (where applicable), and all subject-related documents were submitted to the institutional ethics committee and approved prior to study initiation. The study will be conducted in accordance with the Declaration of Helsinki and relevant national and institutional regulations.

The investigators will submit periodic progress reports to the ethics committee as required. Any protocol amendments or changes related to informed consent procedures will be reported to and approved by the ethics committee before implementation, unless such changes are necessary to eliminate an immediate and direct risk to participants, in which case the ethics committee will be notified promptly. The ethics committee will also be informed in writing upon study suspension or completion.

Given the retrospective nature of the study and the use of existing identifiable data without commercial interest, a partial waiver of informed consent was approved by the ethics committee. For participants who can be successfully contacted, investigators will first provide oral information about the study and document the communication. If participants or their legal representatives subsequently return for clinical follow-up, written informed consent will be obtained. For participants who cannot be contacted, the requirement for informed consent is waived in accordance with ethical and regulatory guidelines.

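### The 400-patient sample size is justified for a logistic mortality model of at most 15 predictors that the analysis plan does not specify, so the claimed stability is unsupported for primary outcome 3

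*Combined protocol and SAP*

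**What the plan says.** Under Sample size estimation, the mortality component is "designed to include no more than 15 candidate predictors in the final multivariable logistic regression model". The criterion is "at least 10 outcome events per predictor", which leads to "a minimum of 150 death" events; this number is presented as what makes the model stable and interpretable. From the centres' historical data, "the in-ICU mortality rate among patients with ARDS is approximately 37.5" per cent, and so "the total target sample size for this study is estimated to be approximately 400 patients". The 15 predictors are not named, and no rule is given for reducing the collected variables to 15.

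The Statistical Analysis Plan describes three analyses that bear on mortality:

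- A multivariable logistic regression of variables for agreement between recommended and actual treatment, together with six anatomical imaging features. It reports adjusted odds ratios. Secondary Outcome Measures lists the association of treatment concordance with 28-day in-hospital mortality.
- Mortality risk prediction, in which severity class and treatment information are added in turn to a base set of inputs that is not listed.
- A LASSO, in which "regression will be applied to all structural, pathological, and intervention-related variables", as an aid to interpretation. No limit is set on the number of variables.

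Prediction of 28-day in-hospital death is the third primary outcome. The Primary Objective describes a model that combines quantitative CT features with clinical characteristics and names mortality among the events to be predicted. Sample Size and Data Partitioning gives "Training set: 276 cases", 69 for internal validation and 55 for external testing. Preliminary Image Processing instead gives a 60/20/20 split.

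**The concern.** Events per predictor describes one particular model fitted to one particular data set. To use it, a reader must know which model is meant, how many predictors were considered before any selection, and how many deaths are in the data used for fitting. The plan settles none of the three for mortality prediction.

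The phrase about candidates in the final model runs two counts together. If 15 is the number considered, the denominator is right. If 15 is the number left after outcome-driven selection from a larger pool, the ratio of 10 is overstated, because the variables that were tried and dropped also contribute to overfitting.

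The whole sample size rests on this one calculation, as does a promise about the model behind a primary outcome. The data are retrospective and the outcomes already exist, so a predictor list left open can be shaped by them.

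**Working it through.** **1. Reproduce the plan's figure.** Inputs from Sample size estimation: 15 predictors, 10 events each, 37.5% mortality.

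- Deaths: 15 × 10 = 150.
- Patients: 150 / 0.375 = 400.

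Both match. The calculation puts all 400 patients into one fit.

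**2. Look for the sized model in the Statistical Analysis Plan.**

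| Analysis | Predicts mortality? | Logistic, at most 15 predictors? |
|---|---|---|
| Agreement variables plus six anatomical features | No; a secondary association analysis | Yes, if 1 to 5 agreement variables are assumed (five modalities): 7 to 11 terms |
| Mortality risk prediction with sequential additions | Yes | Not stated; base inputs not listed |
| LASSO | Used for interpretation | No cap stated |

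No row is a mortality prediction model of the kind that was sized. The first row does satisfy the rule on all 400 patients: 150 / 11 = 13.6 to 150 / 7 = 21.4 deaths per term. It is not the model scored in primary outcome 3.

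**3. Count deaths in the data used for fitting, granting exactly 15 predictors.** Expected deaths = cases × 0.375.

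| Cases used to fit | Expected deaths | Deaths per predictor |
|---|---|---|
| All 400 | 150 | 10.0 |
| Training plus internal validation, 276 + 69 = 345 | 129.4 | 8.6 |
| Training, 276 | 103.5 | 6.9 |
| Training under the 60% split, 240 | 90 | 6.0 |

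Only a fit to all 400, including the external test cases, reaches ten.

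**4. Illustrate the effect of the candidate count.** The Data collection section lists age, sex and BMI (3), named comorbidities (6), etiology (1), respiratory support items (3), vital signs (5), laboratory values (14), ventilator or high-flow settings (4) and scores (2). The sum is 38, or 33 if the comorbidities are pooled into one. If all were candidates, 150 deaths would give 150 / 38 = 3.9 each, or 150 / 33 = 4.5. The condition matters: no section says that all of them are candidates for the mortality model.

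**The case against.** Several points on the other side are sound.

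- **The text may already cap candidates.** Sample size estimation does use the word candidate, and a cap of 15 on candidates is what the rule needs. This reading is open. It is not the only one, and the Statistical Analysis Plan contains nothing that would settle it.
- **There is a logistic model in the plan.** The concordance regression probably falls within 15 terms and meets ten events per term on 400 patients. That stands, so it would be wrong to say that no analysis fits the description. But the sample size section speaks of mortality prediction, and this regression estimates an association.
- **The final model could be refitted on all 400.** That would restore 10.0. The plan does not say so, and Sample Size and Data Partitioning keeps the external test cases out of model development.

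A reader might also infer that the mortality model uses 38 or more inputs, that it has about four deaths per input or fewer, and that stability has been shown to fail. The documents do not support this. The 38 items are a data-collection list. The sentence "The multimodal features are then concatenated and fed into the prediction head" goes on to name severity and subtypes as its targets, not mortality. The LASSO sentence does not mention vital signs, laboratory values, comorbidities or scores. Ten events per predictor is a rule for unpenalised regression, so a low ratio says no more about a LASSO or a network than the plan's ratio of 10 does. Any loss of discrimination or calibration from selection would depend on effect sizes and a selection method that the plan does not give, so none is claimed here.

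**Conclusion.** The concern holds as a mismatch between the justification and the analysis. The arithmetic is correct, but it belongs to a mortality prediction model that the Statistical Analysis Plan does not specify. The claim of stability and interpretability is therefore unsupported for the model scored in primary outcome 3. Unsupported does not mean disproved, since the inputs of that model are undefined.

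The size that needs no assumption about candidate numbers is 6.9 deaths per predictor instead of 10, at exactly 15 predictors in the 276 training cases (6.0 under the 60% split). It rests on the plan's 37.5% applying equally to the training cases. That rate is in-ICU mortality, whereas the outcome is 28-day in-hospital mortality, and the documents do not give the latter rate. The figure of 3.9 is an illustration of what would follow if all 38 collected items were candidates; it is not an estimate for this plan.

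**What to change.** In Sample size estimation, take one of two routes:

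- **(a) Fix the model.** Name at most 15 candidate predictor parameters, counted before any selection (each category or spline term counts as one) and fixed before outcomes are examined. Add that logistic model to the Statistical Analysis Plan as the mortality model the sample size covers. State the expected deaths per predictor in the data used to fit it, not in all 400.
- **(b) Withdraw the claim.** If selection is to be data-driven, state the actual number of candidates and the resulting ratio, and delete the clause promising stability and interpretability. The number must be the sponsor's own count; the 38 used above should not be copied in.

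Under either route, add a sentence saying that the events-per-predictor rule does not cover the multimodal network or the LASSO.

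The cost is wording, a fixed predictor list under route (a), and a stated figure that looks less favourable. No more patients are needed.
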